10.5. Sub-groups

Analysis of disease control will include a stratified assessment of whether or not subjects reach disease control by subjects who enroll with/without fulfilling all of the eligibility criteria. Further details are provided in [Section 13.1](#).

10.6. Covariates

No covariates will be included in the primary analyses.

10.7. Multicenter studies

The main analyses will not be adjusted for study center.

10.8. Multiple comparisons

No adjustments for multiplicity will be employed. Multiple testing issue is acknowledged for the numerous treatment group comparisons in safety analyses (one comparison for each type of AE, each laboratory parameter etc.), but nothing will be explicitly adjusted.

10.9. Timing of analyses

The final analysis will be performed after the database is locked. However, statistical programming for the final analysis based on blinded (mock) data will commence before database lock.

10.10. Interim analyses

There is no planned interim analysis for this study.

10.11. Software

Data analyses will be performed with SAS® version 9.4 or higher.

10.12. Reporting conventions

10.12.1. General

Range or min, max values will be rounded to the precision of the original value, means, and medians will be rounded to 1 decimal place greater than the precision of the original value, and SDs or SEs will be rounded to 2 decimal places greater than the precision of the original value. Percentages will generally be rounded to the nearest whole number (trailing decimal zeroes are not displayed).

10.12.2. Tables

All summary tables will be structured with a column for each treatment group, unless treatment group is clearly irrelevant for the summary (e.g., reasons for screening failures). All summary tables will be annotated with the analysis set and total population size relevant to that table. Mock tables are included in [section 18](#).

10.12.3. Listings

Listings will generally present the data as it appears on the eCRFs without any further grouping or pooling as used in the analyses. In general, a listing will be developed for each eCRF utilized in the study; any derived values used in table or figure analysis will be reported at the subject level in the associated listing.

Listings will be formatted as separate Excel files. Most listings will not be included in the main body of the Statistical Analysis Report (SAR), except for (at least) the listings of serious adverse events and adverse events of special interest.

Any listings that are “by subject” have all the results of one subject in one row, with a space reported between each subject entry. Any listings that are “by subject by visit” have one row per subject per visit. Otherwise, different results of one subject may be organized to separate rows in some other way (e.g., one medical history element per row). Listings that include multiple rows per subject will only report the first occurrence of repeat variables in the data presentation. If possible, all entries for a subject will be maintained on the same page and will only split entries between pages if necessary due to space limitations. All listings are sorted by the site, subject number and treatment group.

11. Summary of study population

11.1. Subject disposition

Subject disposition will be presented for the ITT set. Summaries will include the number and percentage of subjects also in the Safety Evaluable set, completing the study, and discontinuing early by the reason for discontinuation by treatment group and over all subjects combined.

11.2. Demographic and other baseline characteristics

Demographics and baseline characteristics will include descriptive statistics of age, race, gender, height (cm), weight (kg), ethnicity, educational level, severity of BP (mild or moderate), total BPDAI activity score, total BPDAI skin blister score and total BPDAI skin urticarial score, total BPDAI mucosal activity score, total BPDAI damage score, total BPDAI-VAS score. Age will be calculated relative to the date of informed consent using birth year from the CRF. Each of these variables will be summarized by treatment group and over all subjects combined for the ITT population.

11.3. Medical history

Medical history elements will be coded to a Preferred Term (PT) and a System Organ Class (SOC) using the Medical Dictionary for Regulatory Activities (MedDRA). Medical History will be presented in a listing to include concomitancy (resolved or ongoing).

11.4. Prior and concomitant medications

Prior and Concomitant medication data will be collected throughout the study on the Prior and Concomitant Medications eCRF page. The start and stop dates for each medication will be compared to

Version: 1.0

Protocol version: 4.0

the **date of randomization** to allow them to be classified as prior and concomitant. Prior medications are medications with start and stop dates prior to the date of randomization. Other medications are considered concomitant.

If medication start and/or stop dates are missing or partial, the dates will be compared as far as possible with the date of randomization. Medications will be assumed to be concomitant, unless there is clear evidence (through comparison of partial dates) to suggest that the medication stopped prior to the date of randomization. If there is clear evidence to suggest that the medication stopped prior to randomization, the medication will be assumed to be prior.

Medications will be coded with the World Health Organization (WHO) drug dictionary and mapped to Anatomic Therapeutic Chemical (ATC) drug class (level 1) and drug name. Prior and concomitant medications will be presented in a listing to include all medications by generic name and verbatim name.

Prior topical steroid treatment will be collected on the Steroid Treatment eCRF. Data as reported on the CRF will be presented in a listing.

11.5. Treatment compliance

As the study agent is administered under direct supervision of the study staff, no problems with treatment compliance are anticipated. Therefore, treatment compliance will not be analyzed separately; study drug administration will be presented in a listing.

11.6. Protocol deviations

Subject-specific protocol deviations will be summarized in a listing to include category (minor, major) and type (GCP, protocol). Categories of protocol deviations are defined in the Protocol Deviation Plan (see study protocol section 13.3).

12. Safety analyses

The Safety Evaluable Analysis Set will be used for all analyses and tables of safety data.

12.1. Adverse events

All subjects who have given informed consent will be evaluated for AEs. AEs will be reviewed, documented, and reported as required at each visit, beginning at screening. All AEs that occur after the time of treatment with the study drug will be considered Treatment Emergent AEs. All reported terms (investigator descriptions) for AEs will be encoded according to the Medical Dictionary for Regulatory Activities (MedDRA). As SAE is a type of AE, all analyses of AEs will also include SAEs.

Summaries that are displayed by system organ class and preferred terms will be ordered by descending incidence of system organ class and preferred term within each system organ class. Summaries of the following types will be presented:

- Overall summary of number of unique TEAEs and treatment-emergent SAEs and subject incidence of TEAEs meeting various criteria;
- Subject incidence of TEAEs by MedDRA system organ class and preferred term;
- Subject incidence of TEAEs by relationship to study drug, MedDRA system organ class, and preferred term

Version: 1.0

Protocol version: 4.0

At each level of summarization (eg, any AE, system organ class, and preferred term), subjects experiencing more than one TEAE will be counted only once. In the summary of TEAEs by severity grade, subjects will be counted once at the highest severity reported at each level of summarization; in the summary of TEAEs by relationship, subjects will be counted once at the closest relationship to study drug.

Adverse event data will be presented in data listings by subject, treatment group, and event. All deaths during the study will be listed by subject, to include the primary cause of death. Serious AEs and AEs leading to discontinuation of the study drug will be presented in separate data listings. A listing of AEs that qualify as adverse of special interest (AESI) will also be reported; per protocol, an AESI includes events of:

- [REDACTED]
- [REDACTED]
- [REDACTED]

12.2. Laboratory evaluations

For each laboratory test (hematology, chemistry, coagulation, screening serology, and urinalysis), the parameters will be presented in data listings by subject, treatment group, and collection date. Normality interpretation (Normal, High, Low, Panic High, Panic Low) will be obtained from the Clinical Status assessment from the central lab (see Data Transfer Plan section 14 – EDF-Format). Laboratory measurements identified as abnormal for hematology, chemistry and coagulation will be presented separately by subject, laboratory test, and unit in individual data listings.

12.3. Vital signs

Results of vital sign measurements will be presented in a data listing.

12.4. Physical examination

Results of the physical examination and targeted physical examination will be presented in a data listing.

12.5. 12-lead ECG

Results of the 12-lead ECG will be presented in a data listing.

12.6. Pregnancies

No pregnancies are expected to occur during the study. If any, these will be listed without any quantitative analysis.

13. Efficacy analyses

The ITT set will be used for the main analyses of efficacy. Efficacy summaries will focus on descriptive summaries of essential study endpoints.

13.1. Disease control without rescue therapy

The number and percent of subjects who did or did not experience disease control will be presented by treatment group; additionally, the number and percent of subjects who achieved disease control without the need for rescue therapy as well as the number and percent of subjects who required rescue therapy

Version: 1.0

Protocol version: 4.0

will be reported by treatment group. The same analysis will be assessed stratifying by those subjects who fulfilled all eligibility criteria and those who did not as determined by the Inclusion/Exclusion criteria CRF. Listings will be included that present the daily SOC disease assessments used to determine disease control as well as the disease control and rescue therapy classifications for each subject.

13.2. Time to disease control

According to the study protocol, disease control is evaluated on a daily basis as part of Standard of Care, and the date of disease control is explicitly recorded in the eCRF.

For subjects who achieve disease control, the time to disease control will be calculated as:

$$\text{Time to disease control (days)} = \text{Date of disease control} - \text{Date of Visit 2 (Baseline (Day 1))} + 1$$

In cases of **study discontinuation** for whatever reason before achieving disease control, or those who do not experience disease control and reach end of study, subjects will be censored at their date of study completion/discontinuation. The time to disease control is calculated as:

Time to disease control (days)

$$= \text{Date of study completion/discontinuation} - \text{Date of Visit 2 (Baseline (Day 1))} + 1$$

Time to disease control will be presented in a listing.

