5.4.2 HANDLING OF PARTICIPANT WITHDRAWALS

Subjects will be encouraged to complete the study and all assessments. Subjects may voluntarily withdraw at any time, and the investigator may discontinue individual subjects from the study at any time.

Approximately 30 subjects will be enrolled in the study with the intent of obtaining 27 evaluable subjects, assuming a 10% dropout rate. Subjects who discontinue or are unblinded prior to treatment Week 1 may be replaced. Subjects who withdraw or are withdrawn during screening will be replaced.

Subjects who have received at least 1 dose (400 mg) but are withdrawn or withdraw from the study will be encouraged to complete the EOT visit procedures and the Safety Follow-up call. The primary reason for study discontinuation will be documented on the case report form (CRF).

Subjects that are withdrawn at the end of Week 3 of treatment due to lack of disease control will perform all EOT visit procedures and the Safety Follow-up call. The primary reason for withdrawal will be documented on the CRF.

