7.3.3.4 End of Treatment Visit/Visit 5/Week 3 (Day 21 ± 2)

The EOT visit should be conducted at any time during the study once the subject has achieved disease control, as assessed by the investigator or at the time of withdrawal (see [Section 5.4.1](#)). This visit can be performed outside the weekly visit and in place of the next scheduled visit. If a previously completed weekly visit was performed within 2 days of the EOT visit, then only the procedures unique to the EOT visit must be performed.

Subjects that do not reach disease control by treatment Visit 5/Week 3 (Day 21 ± 2) (see [Section 5.4.1](#)) will be discontinued and required to perform all EOT procedures.

- Collect PK and biomarker samples (see [Section 17.8.1](#))
- Perform specified assessments:
 - BPDAI (see [Section 7.1.1.3.1](#))
 - BPDAI-VAS (see [Section 7.1.1.3.2](#))
 - DLQI (see [Section 7.1.1.3.3](#))
 - Assessment of disease control (see [Section 7.1.1.3](#))
 - Skin biopsy (optional) (see [Section 7.1.1.3.4](#))
 - MoCA (see [Section 7.1.1.3.5](#))
- Collect clinical laboratory tests (see [Section 7.1.1.2.6](#))
 - Hematology
 - Chemistry
 - Coagulation
 - Urinalysis
 - Serum Proteins
 - Anti-BP180 antibodies
 - Pregnancy test in WOCBP
- Perform full physical examination
- Perform 12-lead ECG
- Collect vital signs
- Review concomitant medications
- AE reporting and evaluation
- Study agent and topical steroid dispensing/administration
- Study agent accountability
- Review and document daily SOC disease assessments performed since the previous study visit, as available
- Documentation of confirmation of histological BP diagnosis per the S2k Guideline for the Diagnosis of Pemphigus Vulgaris/Foliaceus and Bullous Pemphigoid ([Schmidt 2015](#)) for potential participation in the follow-on open-label, 12-month treatment study

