7.3.4 FOLLOW-UP

7.3.4.1 Fourteen (14)-Day Safety Follow-Up: (Day 14 ± 3) Following Discontinuation of Study Agent

All subjects will be contacted via telephone 14 days ±3 days after EOT visit to assess safety. A review of all ongoing AEs and concomitant medications will be performed.

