7.3.6 TRIAL COMPLETION AND END OF TRIAL

Trial completion is defined as the end of participation for each enrolled subject. A Safety Follow-up call will be performed (see [Section 7.3.4.1](#)) and trial completion will occur after the follow-up call. The Safety Follow-up call should occur 14 ± 3 days following the EOT visit, independent of the actual study day number. If a subject has withdrawn consent, trial completion will be at the time of consent withdrawal and no further procedures will be performed (also see the [Schematic of Study Design](#) for additional information).

The end of the trial will occur following the last subject's last visit. The approximate duration to conduct the trial to support full recruitment is approximately 15 months.

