15 SCHEDULE OF EVENTS

	Screening/ Baseline		Treatment			EOT	Safety Follow-up ⁶
Visit Number/Name	1	2	3 ¹	4 ²	Unsched. Visit ⁴	5 ³ / EOT ⁵ 21 or Dis. Control ±2 ³ Up to 3	Follow-up EOT + 14 ±3 Up to 5
Day	-3 to 0	1	7	14			
Window (days)			±2	±2			
Week			1	2			
Informed consent ⁷	X						
Demographics	X						
Medical history	X						
Inclusion/exclusion criteria	X	X ⁸					
Physical examination	X					X	
Targeted physical examination		X	X	X			
Vital signs	X	X	X	X		X	
12-lead ECG	X						X
BPDAI	X	X	X	X			X
BPDAI-VAS	X	X	X	X			X
Skin biopsy ⁹	X						X
Blister fluid collection		X	X				
Randomization		X					
Topical steroid assessment ¹⁰		X			X		
Administration of study agent		↔					
Administration of topical steroid therapy		↔					
Assessment of disease control ¹¹			X	X	X	X	
Rescue therapy assessment ¹²			X	X	X		
MoCA		X					X
DLQI		X					X
Laboratory tests ¹³	X	X	X	X			X
Serum protein sample collection	X	X	X	X			X
Anti-BP180 antibodies sample collection	X	X	X	X			X
Pregnancy test (in WOCBP only) ¹⁴	X						X
PK blood sample ¹⁵		X	X	X			X
Biomarker plasma aliquots ¹⁶		X					X
Study agent accountability ¹⁷		X	X	X	X		X
Adverse events	X	X	X	X	X	X	X
Concomitant medications ¹⁸	X	X	X	X	X	X	X
Documentation of confirmation of histological BP diagnosis						X	
Trial completion							X

Notes:

1. At Visit 3/Week 1, all subjects that have not achieved disease control will be assessed for rescue therapy. Rescue therapy is indicated if the subject worsens at any time during the study or fails to improve by the end of Week 1, as assessed by the investigator.
2. After Visit 3/Week 1, subjects will continue to be assessed weekly until disease control/EOT visit.
3. Subjects that do not reach disease control by the end of Week 3/Visit 5 will be discontinued and required to perform all EOT visit procedures. Visit 5 will be the EOT visit for subjects that reach Week 3, and all EOT procedures will be performed. The visit window of \pm 2 days is applicable only for subjects that did not yet reach disease control and are being discontinued. Subjects that reach disease control should complete EOT on the same day in which disease control is confirmed.
4. Unscheduled visits can be performed during the study for assessment of AEs, concomitant medications, or disease control, but are not to be conducted in place of a scheduled weekly visit.

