8.2. Secondary endpoints

1. Safety as assessed by the incidence, seriousness, and severity of adverse events (AEs).
2. Time to disease control by treatment day/week.
3. Time to rescue therapy by treatment day/week.
4. Change from baseline in BPDAI score by treatment week and at disease control.
5. Change from baseline in pruritus as evaluated by the BPDAI-VAS by treatment week and at disease control.
6. Change from baseline in skin biopsy [REDACTED] levels at disease control.
7. Evaluation of total cumulative steroid exposure at baseline, by treatment week and at disease control.
8. Evaluation of maximum daily steroid dose at baseline, by treatment week and at disease control.

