13.3. Time to Rescue therapy

Time to rescue therapy will be defined as the time to the start date of the first reported administration of steroid treatment, per the Steroid Treatment CRF, that is reported as “Rescue” for the Timing of Use variable.

For subjects who **will be positively assessed for the need of rescue therapy**, the time to rescue therapy will be calculated as:

Time to rescue therapy (days)

$$= \text{Start date of first rescue treatment} - \text{Date of Visit 2 (Baseline (Day 1))} + 1$$

In cases of **study discontinuation or a subject completing study without the need for rescue therapy**, the time will be calculated as follows:

Time to rescue therapy (days)

$$= \text{Date of study completion/discontinuation} - \text{Date of Visit 2 (Baseline (Day 1))} + 1$$

Time to rescue therapy will be presented in a listing.

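### SAP 13.3 runs time to rescue for unrescued completers to the safety call, adding 11–17 days after study agent has stopped; SAP 13.2 leaves the end date of a Week 3 non-controller open

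*SAP*

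**What the plan says.** SAP 13.2, for time to disease control, takes subjects who discontinue before control together with "those who do not experience disease control and reach end of study, subjects will be censored at their date of study completion/discontinuation". SAP 13.3, for time to rescue, uses the same end date in cases of discontinuation or of "a subject completing study without the need for rescue therapy", but does not describe the resulting value as censored. In both sections the time is the end date minus the Visit 2 (Day 1) date plus 1, and the result goes into a listing. The SAP does not define study completion.

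The protocol does. Under section 7.3.6, "trial completion will occur after the follow-up call", and that call comes 14 ± 3 days after EOT. Section 7.3.4 places the call after study agent has been discontinued and limits its content: "A review of all ongoing AEs and concomitant medications will be performed".

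The date of EOT depends on the subject:
- **Controlled subjects** (Schedule of Events, note 3): "Subjects that reach disease control should complete EOT on the same day in which disease control is confirmed".
- **Subjects not controlled by Week 3** (section 7.3.3.4, Day 21 ± 2): they "will be discontinued and required to perform all EOT procedures". Section 5.4.2 adds that subjects withdrawn then "due to lack of disease control will perform all EOT visit procedures and the Safety Follow-up call".

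SAP 8.2 names the rescue endpoint as "Time to rescue therapy by treatment day/week", and time to disease control is worded in the same way.

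**The concern.** A censored time should end when the subject was last observed for the event under the conditions that the endpoint describes. For a controlled, unrescued completer, SAP 13.3 goes past that point. The extra days come after study agent has stopped and include no scheduled assessment of rescue or of disease control. Because 13.3 does not call the value censored, an end-of-follow-up date is labelled as a time to rescue.

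SAP 13.2 does say censored. Its weakness is that a Week 3 non-controller has both a discontinuation date and a completion date, and the text does not choose between them. Two programmers could produce different values for the same subject.

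The protocol (section 10.4.3) planned Kaplan-Meier curves for both endpoints. After enrolment ended at six subjects, the SAP kept only listings. Those listings are now the sole derived output for two named secondary endpoints, and with six subjects each value will be read individually.

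**Working it through.** **Inputs**
- Time = end date − Visit 2 date + 1 (SAP 13.2, 13.3). Visit 2 is Day 1, so the result is the study day of the end date.
- Call = EOT + 14 ± 3 days, that is EOT + 11 to EOT + 17 (Protocol 7.3.6).
- Controlled on day d: EOT = d (Schedule of Events, note 3).
- Not controlled at Week 3: EOT = Day 21 ± 2, that is Day 19–23 (Protocol 7.3.3.4).

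**The plan's own figure.** Protocol 4.1 gives participation of about 5 weeks. Three weeks of treatment plus the 14-day call is (21 + 14)/7 = 5.0 weeks. This reproduces the figure and confirms that participation is counted to the call.

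**Time to rescue, controlled and unrescued completer.** The listed value is d + 11 to d + 17.

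| Control (= EOT) | Listed under 13.3 (nominal) | Time to EOT | Share after study agent stopped |
|---|---|---|---|
| Day 7 | 18–24 (21) | 7 | 11/18 to 17/24 = 61–71% |
| Day 14 | 25–31 (28) | 14 | 11/25 to 17/31 = 44–55% |
| Day 21 | 32–38 (35) | 21 | 11/32 to 17/38 = 34–45% |

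The last possible treatment day is 21 + 2 = Day 23. At the nominal call date the listed time passes Day 23 for control from Day 10 on (10 + 14 = 24). At every permitted call date it does so from Day 13 on (13 + 11 = 24).

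**What is assessed in the extra days.** Protocol 7.3.3 lists assessment of the need for rescue at Weeks 1 and 2 and at unscheduled visits, and assessment of disease control at those visits and at EOT. Protocol 7.3.4 lists neither at the call.

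**Time to disease control, Week 3 non-controller.**
- Discontinuation date taken as EOT: Day 19–23, 0 extra days.
- Completion date: 19 + 11 = Day 30 to 23 + 17 = Day 40 (nominal 21 + 14 = 35), 11–17 extra days, all after the last disease-control assessment.

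The same two readings apply in 13.3 if that subject was never rescued.

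**Day count.** SAP section 5 defines both times as days from randomization, without the +1. Randomization is at Visit 2 (Protocol 7.3.2.1), so section 5 gives one day less. Control on Day 7 is 6 days under section 5 and 7 under 13.2; rescue starting on Day 8 is 7 days under section 5 and 8 under 13.3.

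**The case against.** The best defence of 13.3 is that following unrescued subjects to last contact may be intended. Protocol 6.1.4 allows rescue for worsening at any time during the study. SAP 13.3 defines the event as the first steroid marked as rescue on the Steroid Treatment CRF, with no cut-off at EOT. The call reviews concomitant medications, so a later steroid could be found. On that reading the event window and the end date match. The endpoint's reference to treatment day and week could describe the reporting unit and need not exclude later days.

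Much of this stands. A reader might infer that rescue after EOT cannot be recorded, and the documents do not support that. But the SAP nowhere says that the window is meant to reach the call. SAP 13.4 ties its own disease-control summary to the EOT visit and Weeks 1–3. Even on the defence's reading, the unrescued value is a censored one and 13.3 should say so.

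For 13.2, a reader might infer that the time of every non-controller runs to the safety call. The text does not show that. Failure to reach control in three weeks is a listed reason for withdrawal (Protocol 5.4.1), so a discontinuation date near Day 21 is a natural reading and adds nothing. The later date is also possible: SAP 10.1 describes all six subjects as completing the study, and Protocol 7.3.6 defines completion for every enrolled subject.

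Three smaller points also stand. The documents show these days to be off study agent only; steroid use after EOT is not specified. The listing layouts are redacted and may already mark censoring. Other displays let a reader recover the true dates: the daily assessments and rescue classifications (SAP 13.1) and the steroid figure and listing (SAP 13.7).

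**Conclusion.** The point holds for SAP 13.3. As written, a controlled, unrescued completer is listed with 11–17 days after study agent stopped and after the last scheduled rescue assessment, and the value is not called censored. For SAP 13.2 the finding is an ambiguity of 0 or 11–17 days. The one-day mismatch with section 5 is a wording matter.

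The 11–17 days assume that study completion in the SAP has the meaning given in protocol version 4.0, which the SAP cites, and that the call fell within its window. Outcomes are not in the documents, so between 0 and 6 subjects are affected, and the 13.2 part may affect nobody.

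The impact is minor. A reader might infer that the efficacy result is distorted. It is not: the primary proportion does not use these times, and the SAP plans no curve, test or summary of them. What remains is listed values that would not agree with the neighbouring displays. That is worth correcting because the correction is cheap.

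**What to change.** - **SAP 13.2:** censor subjects without control at the EOT visit, or at the last disease-control assessment if that is earlier or no EOT visit was done.
- **SAP 13.3:** censor unrescued subjects at the EOT visit, or at the last assessment if there was none, and state that the value is censored. If the sponsor intends rescue to count up to the call, say so and list any post-EOT rescue separately.
- **Both listings:** mark censored values, if the redacted layouts do not already do so.
- **SAP section 5:** use the same +1 day count as 13.2 and 13.3.

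The cost is one end date in two formulas, a mark and a wording correction; the EOT date is already collected. There are two downsides. Subjects controlled early get short rescue times that could be misread as early rescue unless they are marked. And unless it is listed separately, a steroid labelled as rescue that starts after EOT would no longer set the 13.3 time and would appear only in the steroid listing.
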